8.4 Selection of Trial Population

8.4.1 Inclusion Criteria

Only patients fulfilling all of the following criteria should be randomized in the present trial:

- [1] Male or female subjects aged between 14 and 75 years inclusive on the date of consent
- [2] Diagnosis of acute, uncomplicated rhinosinusitis defined at screening Visit 1 and at Visit 2 as:
 - a) major symptom score (MSS) assessed by the patient ≥ 8 and ≤ 12 points for the following: rhinorrhea/ anterior discharge, postnasal drip, nasal congestion, headache, and facial pain/pressure, whereupon the nasal congestion is mandatory and no more than 3 of the 5 symptoms are rated as severe
 - b) individual score for facial pain/pressure ≥ 1 (mild) and ≤ 2 (moderate)
 - c) presence of symptoms ≤ 3 days prior to screening visit
- [3] For adults (≥ 18 years): Informed consent to participate in the trial provided in written form; For adolescents (≥ 14 - < 18 years): own subject informed consent/ assent to participate in the trial and the informed consent from all parent(s)/ legal guardian(s) provided in written form.

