9.1 Trial Specific Efficacy Assessments

The following trial specific efficacy assessments will be performed by the PATIENT:

➤ Major Symptom Score (MSS)

The MSS combines the 5 most relevant symptoms of rhinosinusitis based on expert clinician recommendations^{1, 21, 22} (**rhinorrhea/ anterior discharge, postnasal drip, nasal congestion, headache, and facial pain/pressure as reported by the group of Meltzer²¹ and Revicki et al.²²**) and has been employed as primary efficacy criterion in several clinical trials¹.

Assessment of symptom severity. The patient will rate the severity of each of the five symptoms of the MSS using a four-point rating scale of increasing severity (⊙ = none/not present, ① = mild, ② = moderate, ③ = severe).

The MSS will be assessed by the patient at screening (Visit 1) and immediately before randomization (Visit 2; this will constitute the baseline value). The investigator will transcribe both patient’s MSS assessments into the CRF.

Thereafter, the patient will document the MSS in the patient diary once a day before intake of the morning dose, starting with Day 2 until Day 14 (last day of treatment or earlier in case of drop-out).

The last MSS will be assessed by the patient during Visit 6 and transcribed into the CRF.

➤ **Sino-Nasal Outcome Test (SNOT-22) questionnaire**

SNOT-22 will be assessed by the patient in the patient diary on Day 1, Day 7 and Day 14.

SNOT-22 will be part of the patient diary printed on no-carbon copy paper (one top page and a second no-carbon copy page). The patient must complete the first SNOT-22 in the patient diary during Visit 2, after the investigator explained unclear terms and answered all patient's questions.

The following trial specific efficacy assessments will be performed and documented by the INVESTIGATOR:

➤ **Investigator's assessment of the overall response to treatment**

The investigator will assess the overall response to treatment at each visit after baseline: on days 4 (Visit 3), 7 (Visit 4), 10 (Visit 5), and 15 (Visit 6).

The investigator will rate the response to treatment using a five-point rating scale: ① = major deterioration, ② = minor deterioration, ③ = no change, ④ = minor improvement, ⑤ = major improvement.

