5.4 Statistical Basis for Sample Size

The sample size is calculated in respect of the primary endpoint. For the calculation of sample size, the following parameters were taken into consideration based on data published by Jund et al. (2015)¹:

α	= 0.05 (two-sided)
β	= 0.20 (power = 80%)
mean MSS change (test)	= 5.4
mean MSS change (placebo)	= 4.5

Standard deviation	= 3.4
Randomization ratio	= 1 (1:1:1:1, 3 doses of test vs. placebo)
Sample size per group:	= 225 patients

The numbers above refer to the FAS.
The number of patients to be randomized in each of the groups is approximately 225.
The total number of patients to be randomized is thus equal to 900.

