7.4 Statistical Analysis of the Endpoints

7.4.1 Statistical Analysis of the Primary Endpoint

Efficacy of the test product will be shown by testing superiority of the three different doses in a hierarchical test procedure from the highest to the lowest dose compared to placebo.

Hierarchical ordered hypotheses will be tested at the type I error rate of $\alpha = 0.05$ (two-sided) until the first non-rejection. No error rate adjustment is required.

The set of hypotheses is as follows:

$$H_{01}: \mu_A = \mu_D \text{ versus } H_{11}: \mu_A \neq \mu_D,$$

$$H_{02}: \mu_B = \mu_D \text{ versus } H_{12}: \mu_B \neq \mu_D,$$

$$H_{03}: \mu_C = \mu_D \text{ versus } H_{13}: \mu_C \neq \mu_D.$$

Where μ_{group} denotes "mean change from baseline in the daily MSS over the entire treatment period" in treatment group (Group A, B, C or D) for the respective strength.

Superiority of the Test treatment over placebo (PL) is confirmed if the p-value is below 5% and a positive treatment effect is shown.

For the primary endpoint, analysis of covariance (ANCOVA) will be carried out using treatment and center as factors and baseline MSS as a covariate.

The SAS procedure PROC GLM will be used for that purpose.

Basically, the following code will be used:

```
proc glm data=primary;  
class treatment center;  
model mss=treatment center baseline_mss;  
estimate 'Group X vs D' treatment 1 -1 ;  
where treatment='X' or treatment='D';  
run;
```

The analysis will be performed for each hypothesis separately, i.e. only data of one active treatment group and the placebo group are included for the respective comparison.

The confirmatory analysis of the primary endpoint will be performed in the FAS.

In addition, the analyses used for the primary efficacy endpoint will be performed in the PPS. This analysis is intended to provide supportive evidence and will be considered descriptive.

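### The confirmatory ANCOVA leaves out the Day 1 SNOT-22, a baseline score already collected, so precision may be lost (optional improvement, not an error)

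*SAP*

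**What the plan says.** **Model.** SAP 7.4.1: "analysis of covariance (ANCOVA) will be carried out using treatment and center as factors and baseline MSS as a covariate". The PROC GLM code in that section has these three terms and no others, and Protocol 10.4 names the same model. Each dose is compared with placebo in a separate fit that uses only the two arms concerned.

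**Baseline MSS.** Protocol 8.4.1 requires, at both Visit 1 and Visit 2, "major symptom score (MSS) assessed by the patient ≥ 8 and ≤ 12 points". The Visit 2 value is the baseline (Protocol 9.1). The score is the sum of five items rated 0 to 3 (SAP 7.3.1.1), so it runs from 0 to 15 and eligible patients can take only five of those values.

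**SNOT-22.** Protocol 9.1: "SNOT-22 will be assessed by the patient in the patient diary on Day 1, Day 7 and Day 14". The Visit 2 procedures in Protocol section 9 place the first questionnaire at the site, ahead of randomization and the first intake. SAP 7.4.2.3 labels Day 1 as baseline and plans descriptive use only. No inclusion or exclusion criterion refers to SNOT-22.

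**Sample size.** SAP 5.4 uses "mean MSS change (test) = 5.4", "mean MSS change (placebo) = 4.5" and "Standard deviation = 3.4", and arrives at 225 per group. It does not mention covariate adjustment.

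**The concern.** Adjustment for a baseline variable narrows the treatment comparison to the extent that the variable predicts the outcome among the patients analysed. Selecting patients on the MSS itself compresses the only patient-level covariate in the model. A second self-rated baseline score is collected from every patient and could explain some of the remaining variance, but it is left out of the confirmatory analysis.

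What is at stake is power. The three doses are tested in a fixed order that stops at the first non-rejection, so any gain in the first comparison also helps the second and third to be reached. Validity is not at issue.

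**Working it through.** **Inputs from the documents.** Two-sided alpha 0.05, power 80%, mean changes 5.4 and 4.5 (difference 0.9), SD 3.4, 225 per group (SAP 5.4); MSS range 8–12 (Protocol 8.4.1).

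**Inputs assumed.** The slope of later MSS on baseline MSS, the spread of baseline MSS within its range, and r, the partial correlation of Day 1 SNOT-22 with the endpoint given center and baseline MSS. The documents give none of these.

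**1. The plan's own figure.** n = 2 × 3.4² × (1.960 + 0.842)² / 0.9² = 224.03, rounded up to 225. Power at 225 per group is 80.2% by the normal formula and 80.0% by the noncentral t. The stated number is reproduced.

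**2. What baseline MSS can explain.** If the values 8, 9, 10, 11 and 12 are equally frequent, the SD is √2 = 1.41; the largest possible SD in that range is 2.0. The endpoint is a change from baseline, so if later MSS has slope b on baseline, the change has slope b − 1. Treating 3.4 as the SD before adjustment, the explained share is (b − 1)² × 1.41² / 3.4².

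| b (assumed) | Share explained | Residual SD | Pairwise power, 225 per group |
|---|---|---|---|
| 0.5 | 0.25 × 2 / 11.56 = 4.3% | 3.33 | 81.7% |
| 0.2 | 0.64 × 2 / 11.56 = 11.1% | 3.21 | 84.4% |
| 0 | 1 × 2 / 11.56 = 17.3% | 3.09 | 86.9% |

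The contribution of baseline MSS is therefore unknown, and it may be small or moderate.

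**3. What SNOT-22 could add.** Here 3.4 is taken as the residual SD after center and baseline MSS. This is a different reading of the same figure from step 2, and the two tables must not be combined. Adding SNOT-22 reduces the SD to 3.4 × √(1 − r²). The equivalent number of extra patients per arm is 225/(1 − r²) − 225. Power is from the noncentral t.

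| r (assumed) | Residual SD | Pairwise power | Equivalent extra patients per arm |
|---|---|---|---|
| 0 | 3.400 | 80.0% | 0 |
| 0.1 | 3.383 | 80.4% | 2 |
| 0.2 | 3.331 | 81.6% | 9 |
| 0.3 | 3.243 | 83.6% | 22 |
| 0.4 | 3.116 | 86.4% | 43 |

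**4. Cost if SNOT-22 predicts nothing.** One error degree of freedom out of more than 400 is lost. The loss of power is below 0.001 percentage points.

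**The case against.** The strongest reply is that nothing here is wrong. Protocol and SAP agree on a pre-specified ANCOVA that adjusts for center and for the baseline of the endpoint itself. Omitting a further covariate does not bias the estimate, inflate the type I error or make the 225 incorrect. All of that stands, and it is why this is only an optional improvement.

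Four stronger readings are tempting, and the documents do not support them.

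- *Precision is certainly lost.* That needs r, which is not given. At r of 0.1 to 0.2 the gain is 0.4 to 1.6 percentage points, and at 0 it is nil. Because patients are selected on MSS, the spread of SNOT-22 may itself be narrowed indirectly.
- *Baseline MSS is nearly useless.* The 4% share holds at one assumed slope; at other plausible slopes it is 11% or 17%. Center may also carry prognostic information. The 8–12 limit is not absolute in the analysis either, because the FAS does not exclude eligibility violators.
- *The trial has exactly 80% power and no margin.* The 80.0% takes 3.4 as the SD of the analysis model. If 3.4 is the unadjusted SD, the planned ANCOVA already does better (81.7% at the 4% share). The documents do not say which is meant.
- *SNOT-22 is a finer measure of the same disease.* The documents describe neither its items nor its response scale.

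It is also fair to say that completion before the first dose is inferred from the order of the Visit 2 procedures and the baseline label. Only the MSS is expressly required just before randomization.

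Finally, the change touches the confirmatory model in a protocol that has four country-specific versions, and whether it needs an amendment would have to be assessed under Protocol 5.3. That is a real administrative cost. There is a route for it: SAP section 4 allows updates for improved methods, and Protocol 10.1 leaves the SAP open until database lock.

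**Conclusion.** The point holds as a missed efficiency option. The confirmatory model adjusts for center and a range-restricted baseline MSS, and leaves out a baseline score that is already collected. Over assumed r from 0 to 0.4 the gain in pairwise power runs from nil to 6.4 percentage points (80.0% to 86.4%), equivalent to 0 to 43 patients per arm. This rests on 3.4 being the residual SD, on the planned difference of 0.9, and on 225 analysed per arm. Nothing in the documents favours one value of r over another.

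The case for acting rests on asymmetry: the possible loss is negligible and the possible gain is useful. Severity: optional improvement, not an error.

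**What to change.** Before unblinding:

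- Add the Day 1 SNOT-22 total as a second covariate: model mss = treatment center baseline_mss baseline_snot.
- State that the Day 1 questionnaire must be completed before the first dose.
- Score it by the item rule in SAP 7.2.5 (worst category for up to two missing items). Replace a total that is still missing with the overall baseline mean pooled over arms; otherwise PROC GLM drops that patient from the FAS analysis.
- Keep the MSS-only model as a sensitivity analysis.
- Record the change against Protocol 10.4.

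The cost is one degree of freedom, a small imputation rule, and a documented pre-unblinding change to the model named in the protocol. No new data are needed, and the endpoint, test order and type I error are unchanged.

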7.4.2 Statistical Analysis of the Secondary Endpoints

7.4.2.1 Time to onset of action defined as first day of active treatment on

which MSS shows statistically significant difference from placebo

This endpoint will be determined as follows:

For each day of assessment (Day 2 until Day 14) of MSS a two-sample t-test (by means of an ANCOVA with factors treatment, center and baseline MSS as covariate) comparing the mean MSS in one active treatment group versus placebo group will be performed. The following hypotheses will be tested:

$$H_{0,g,v}: MSS_{g,v} = MSS_{D,v} \text{ vs. } H_{1,g,v}: MSS_{g,v} \neq MSS_{D,v}$$

For the active treatment groups g (Groups A, B or C) and visits v (from Day 2 to Day 14).

For each hypothesis to test only the data related to the hypothesis will be used.

The earliest day showing a significant difference at level $\alpha = 5\%$ will then be defined as the time to onset of action.

This analysis is deemed to be descriptive and will be performed in FAS and in the PPS.

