10.2.2 Secondary Endpoints

Secondary endpoints are:

- Time to onset of action defined as first day of active treatment on which MSS shows statistically significant difference from placebo
- MSS development over the course of the study
- SNOT-22 by visit and changes versus baseline
- Percentage of responders and non-responders to treatment based on the assessment of overall response to treatment by the investigator.

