6.2 Secondary Endpoints

- Time to onset of action defined as first day of active treatment on which MSS shows statistically significant difference from placebo
- MSS development over the course of the study
- SNOT-22 by visit and changes versus baseline
- Percentage of responders and non-responders to treatment based on the assessment of overall response to treatment by the investigator.

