7.3 Analysis Variables

7.3.1 Efficacy Variables

7.3.1.1 Major Symptom Score (MSS)

The MSS combines the following symptoms of rhinosinusitis based on expert clinician recommendations

- rhinorrhea/ anterior discharge,
- postnasal drip,
- nasal congestion,
- headache, and
- facial pain/pressure.

Assessment of symptom severity. The patient will rate the severity of each of the five symptoms of the MSS using a four-point rating scale of increasing severity (⊙ = none/not present, ① = mild, ② = moderate, ③ = severe).

The MSS is then the sum of the single ratings.

The MSS will be assessed by the patient at screening (Visit 1) and immediately before randomization (Visit 2; this will constitute the baseline value). The investigator will transcribe both patient's MSS assessments from TSSF into the CRF.

Thereafter, the patient will document the MSS in the patient diary once a day before intake of the morning dose, starting with Day 2 until Day 14 (last day of treatment or earlier in case of drop-out).

The last MSS will be assessed by the patient during Visit 6 and transcribed from TSSF into the CRF.

Statistical evaluation of the MSS is described in section [7.4](#).

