7.4.2.2 MSS development over the course of the study

For each day of assessment (Day 1 until Day 15, or up to 3 days later) descriptive statistics (mean, standard deviation, median, minimum and maximum) for the MSS per treatment group will be determined and displayed for the FAS and the PPS.

The mean values will be presented in a graphic containing the curves for all four treatment groups.

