14.2 Efficacy data	
Evaluation of the primary endpoint - Mean change from baseline in daily MSS ANCOVA and superiority test, Treatment A vs D, FAS
 
Evaluation of the primary endpoint - Mean change from baseline in daily MSS ANCOVA and superiority test, Treatment A vs D, PPS
 
Evaluation of the primary endpoint - Mean change from baseline in daily MSS ANCOVA and superiority test, Treatment B vs D, FAS
 
Evaluation of the primary endpoint - Mean change from baseline in daily MSS ANCOVA and superiority test, Treatment B vs D, PPS
 
Evaluation of the primary endpoint - Mean change from baseline in daily MSS ANCOVA and superiority test, Treatment C vs D, FAS
 
Evaluation of the primary endpoint - Mean change from baseline in daily MSS ANCOVA and superiority test, Treatment C vs D, PPS
 
Evaluation of secondary endpoint - Time to onset of action, FAS
 
Evaluation of secondary endpoint - Time to onset of action, PPS
 
Evaluation of secondary endpoint - MSS development of the course of the study, FAS
 
Evaluation of secondary endpoint - MSS development of the course of the study, PPS
 
Evaluation of secondary endpoint - SNOT-22 by visit and change to baseline, FAS
 
Evaluation of secondary endpoint - SNOT-22 by visit and change to baseline, PPS
 
Evaluation of secondary endpoint - Percentage of responders and non-responders, FAS
 
Evaluation of secondary endpoint - Percentage of responders and non-responders, PPS
 
Frequency table for month of inclusion and country in the group of non-responders, FAS
 
Sensitivity analysis - Percentage of responders and non-responders controlled by month of inclusion, FAS
 
Sensitivity analysis - Percentage of responders and non-responders controlled by month of inclusion, PPS

---------------------------	---

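### The onset-of-action rule in SAP 7.4.2.1 takes the earliest of 13 daily two-sided tests without requiring that the difference favour active treatment

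*SAP*

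**What the plan says.** Protocol 10.2.2 lists time to onset of action as a secondary endpoint and defines it as the "first day of active treatment on which MSS shows statistically significant difference from placebo". SAP 6.2 repeats this definition.

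SAP 7.4.2.1 makes it operational. For each active group there is one ANCOVA comparison with placebo per day from Day 2 to Day 14, with treatment and center as factors, baseline MSS as covariate and a not-equal alternative. "The earliest day showing a significant difference at level" 5% then becomes the onset time. The section closes: "This analysis is deemed to be descriptive and will be performed in FAS and in the PPS". SAP 7.2.3 sets 5% for every test unless stated otherwise, and no adjustment is stated for these tests.

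Three other places bear on the point:

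- SAP 7.4.1, for the primary endpoint: superiority "is confirmed if the p-value is below 5% and a positive treatment effect is shown".
- SAP 7.3.1.1: each symptom is rated "using a four-point rating scale of increasing severity" and the MSS is the sum, so a lower MSS is better.
- SAP 7.4.2.2: daily descriptive statistics of MSS per group. "The mean values will be presented in a graphic containing the curves for all four treatment groups".

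SAP 8.1 lists the onset tables by title only, for example "Evaluation of secondary endpoint - Time to onset of action, FAS".

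**The concern.** A two-sided test is significant in either direction. For the primary endpoint the SAP deals with this by adding a direction condition. The next section uses the same two-sided form and leaves the condition out. A programmer working from SAP 7.4.2.1 therefore has a complete rule that never looks at the sign of the difference.

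What is at stake is the meaning of one reported result: a single day per dose, for a listed secondary endpoint. If the earliest significant day is one on which placebo did better, the rule reports the opposite of an onset of benefit under that name. It also stops there, so a later day on which active was significantly better would not be the one named.

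**Working it through.** **Wording, side by side.** Primary endpoint (SAP 7.4.1): p below 5% and a positive effect. Onset (SAP 7.4.2.1, SAP 6.2, Protocol 10.2.2): a significant difference only. No sentence carries the condition from the first to the second. This establishes the gap; the figures below only give its size.

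**Inputs from the documents.** Day 2 to Day 14 is 14 − 2 + 1 = 13 tests per dose. Each is two-sided at 0.05 (critical |z| = 1.96). The sample-size section gives a difference of 5.4 − 4.5 = 0.9, SD 3.4 and 225 per group.

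**The plan's own figure.** The documents state no error rate or power for onset. The sample size reproduces: n = 2 × (1.960 + 0.842)² × 3.4² / 0.9² = 224.03, rounded up to 225. The standard error of a difference is 3.4 × √(2/225) = 0.3206, so 0.9 corresponds to 0.9 / 0.3206 = 2.81 standard errors and about 80% power.

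**Assumptions.** The correlation between the daily test statistics is not given; AR(1) from 0.98 to 0.70 is used. The simulation draws 13 correlated z-statistics per dose, without center or baseline terms (200,000 runs per scenario).

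**No drug effect.** Independent days give an upper reference: 1 − 0.95¹³ = 48.7% of trials name an onset day, and 1 − 0.975¹³ = 28.0% do so if the favourable direction is required. By symmetry, half of the days named by the written rule favour placebo. With correlated days, per dose:

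| AR(1) | Onset day named, SAP rule | of all trials: that day favours placebo | Onset day named, direction required |
|---|---|---|---|
| 0.98 | 11.6% | 5.8% | 5.8% |
| 0.95 | 16.6% | 8.3% | 8.3% |
| 0.90 | 22.5% | 11.2% | 11.4% |
| 0.80 | 30.8% | 15.4% | 15.7% |
| 0.70 | 36.6% | 18.2% | 19.1% |

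The last column can slightly exceed half of the first, because some trials have a placebo-favouring day first and an active-favouring day later. Of the false onsets in the last column, 20% (0.98) to 59% (0.70) rest on exactly one significant day.

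**Effective dose.** The documents give no time course, so shapes are assumed, with n = 225 per arm and SD 3.4 on each day. The denominator is all trials.

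- Effect starts on Day 5 (abrupt 0.9 points; ramp to 1.5; or waning from 1.4 on Day 7 to 0.3 on Day 14): the written rule names a placebo-favouring day in 3.8% to 6.2% of trials at AR(1) 0.95 and 0.70, and in about 3% at 0.98. Most of this comes from Days 2 to 4, which have no effect by construction. At 0.95 and 0.70 a day before Day 5 is named in 7.6% to 11.5% of trials, and half of that is 3.8% to 5.8%.
- Effect starts on Day 2, AR(1) 0.70 / 0.95: constant 0.9 points, 0.0% / 0.0%; ramp to 0.9 by Day 5, 0.4% / 0.4%; linear ramp to 1.5, 1.3% / 1.0%.

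**What the direction condition removes for an effective dose.** The largest fall in the share of trials with a named day is for the abrupt Day 5 start: from 95.7% to 93.5% (2.2 points) at AR(1) 0.95, and 3.0 points at 0.98. A trial loses its day only if none of its significant days favours active, so in every such trial the only significant days favoured placebo.

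**The case against.** The strongest reply is that onset of action plainly means benefit, that the analysis is declared descriptive, and that the daily means and curves in SAP 7.4.2.2 would show a wrong direction in the same report. All of this stands, and it is why the point is minor. It does not close the gap: the intended meaning is not in the rule, and the curves do not change the day that the rule reports.

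Three stronger readings are tempting, and the documents do not support them.

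- A reader might infer that the trial's type I error is inflated. It is not. The confirmatory claim rests on the primary endpoint, which has its own direction condition and fixed order of testing.
- A reader might infer that the plan conceals the lack of adjustment. It does not. SAP 7.4.2.1 and 7.2.3 together fix each daily test at 5% with no adjustment. At most a note to the table is missing, and since SAP 8.1 gives titles only, the content of that table cannot be judged.
- A reader might infer that an effective dose is regularly given a wrong-way onset day. That depends on the assumed start of effect. If the drug acts from Day 2, the share is 0% to 1.3%; the 3% to 6% arises only when the first days carry no effect. A start later than Day 5 would raise it.

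**Conclusion.** The concern holds on the wording: the rule as written can report a day favouring placebo as the onset of action. With no drug effect this happens for a given dose in about 6% to 18% of trials, within the 12% to 37% in which any onset day is named. For an effective dose the figure is about 0% to 6%. These sizes rest on the assumed AR(1) range of 0.98 to 0.70 and, for an effective dose, on assumed effect shapes; the gap itself rests on neither. Severity is minor, because a descriptive secondary result is affected and the primary analysis is not.

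**What to change.** In SAP 7.4.2.1, with SAP 6.2 aligned, define onset as the earliest day with p<0.05 on which the adjusted mean MSS is lower on active than on placebo. Make this as an SAP update before database lock. SAP section 4 allows updates to the analyses, and Protocol 10.1 leaves analysis detail to the SAP. The Protocol definition is silent on direction, so the clause clarifies it and does not contradict it.

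The cost is one clause, with no new data and no new model: the sign comes from the ANCOVAs already planned. Under the assumed shapes, an effective dose gets a named day in up to about 3 percentage points fewer trials, none of which had a significant day favouring active.

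The clause does not deal with repeated testing. With no drug effect, about 6% to 19% false onsets per dose remain. As an option, the onset table could show the daily adjusted differences from placebo with 95% confidence intervals from the same ANCOVAs, so that a reader can recognise a day that stands alone.
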